- □ Community-Based Participatory Research
- □ Deception
- □ Educational/Student Records (e.g., GPA, test scores)
- □ Emergency Use (Single Patient)
- ☐ Gene Transfer
- ☐ Genetic Research
- $\hfill \square$ GWAS (Genome-Wide Association Study) or NIH Genomic Data Sharing (GDS)
- □ Human Cells, Tissues, and Cellular and Tissue Based Products
- □ Individual Expanded Access or Compassionate Use
- □ International Research
- □ Planned Emergency Research Involving Exception from Informed Consent
- □ Recombinant DNA
- □ Registry or data repository creation
- ☐ Stem Cell Research
- □ Suicide Ideation or Behavior Research
- ☐ Survey Research
- □ Transplants
- $\hfill\Box$ Use, storage and disposal of radioactive material and radiation producing devices
- □ Vaccine Trials

For additional requirements and information:

- Cancer Research (MCC PRMC)
- Certificate of Confidentiality (look up "Confidentiality/Privacy...")
- CCTS (Center for Clinical and Translational Science)
- Clinical Research (look up "What is the definition of....)
- Clinical Trial
- Collection of Biological Specimens for Banking (look up "Specimen/Tissue Collection...")
- Collection of Biological Specimens (look up "Specimen/Tissue Collection...")
- Community-Based Participatory Research (look up "Community-Engaged...")
- Data & Safety Monitoring Board (DSMB)

*For Medical IRB: Service Request Form for CCTS DSMB

- Data & Safety Monitoring Plan
- Deception*

*For deception research, also go to the E-IRB Application Informed Consent section, checkmark and complete "Request for Waiver of Informed Consent Process"

- Emergency Use (Single Patient) [attach Emergency Use Checklist] (PDF)
- Genetic Research (look up "Specimen/Tissue Collection...")
- Gene Transfer
- HIV/AIDS Research (look up "Reportable Diseases/Conditions")
- Screening for Reportable Diseases [E2.0000] (PDF)
- International Research (look up "International & Non-English Speaking")
- NIH Genomic Data Sharing (GDS) Policy (PDF)
- Planned Emergency Research Involving Waiver of Informed Consent*

*For Planned Emergency Research Involving Waiver of Informed Consent, also go to the E-IRB Application Informed Consent section, checkmark and complete "Request for Waiver of Informed Consent Process"

• Use, storage and disposal of radioactive material and radiation producing devices

88617 CLOSED

FUNDING/SUPPORT

0 unresolved comment(s)

If the research is being submitted to, supported by, or conducted in cooperation with an external or internal agency or funding program, indicate below all the categories that apply. ①

Not applicable

-Check All That Apply

- □ Grant application pending
- (HHS) Dept. of Health & Human Services
- (NIH) National Institutes of Health
- $\ \ \square$ (CDC) Centers for Disease Control & Prevention

- Federal Agencies Other Than Those Listed Here
- Industry (Other than Pharmaceutical Companies)
- Internal Grant Program w/ proposal
- ☐ Internal Grant Program w/o proposal
- National Science Foundation
- Other Institutions of Higher Education
- Pharmaceutical Company
- □ Private Foundation/Association
- **■** U.S. Department of Education

Other:

Click applicable listing(s) for additional requirements and information:

- (HHS) Dept. of Health & Human Services
- (NIH) National Institutes of Health
- (CDC) Centers for Disease Control & Prevention
- (HRSA) Health Resources & Services Administration
- (SAMHSA) Substance Abuse & Mental Health Services Administration
- Industry (Other than Pharmaceutical Companies) [IRB Fee Info]
- National Science Foundation
- (DoEd) U.S. Department of Education
- (DoJ) Department of Justice or Bureau of Prisons
- (DoE) Department of Energy Summary and Department of Energy Identifiable Information Compliance Checklist
- (EPA) Environmental Protection Agency

Specify the funding source and/or cooperating organization(s) (e.g., National Cancer Institute, Ford Foundation, Eli Lilly & Company, South Western Oncology Group, Bureau of Prisons, etc.):

Add Related Grants

If applicable, please search for and select the OSPA Account number or Electronic Internal Approval Form (eIAF) # (notif #) associated with this IRB application using the "Add Related Grants" button.

If required by your funding agency, upload your grant using the "Grant/Contract Attachments" button.

Add Related Grants

Grant/Contract Attachments

The research involves use of Department of Defense (DoD) funding, military personnel, DoD facilities, or other DoD resources. (See DoD SOP and DoD Summary for details)

Yes
 No

Using the "attachments" button (below), attach applicable materials addressing the specific processes described in the DoD SOP.

DOD SOP Attachments

88617 CLOSED

Additional Certification: (If your project is federally funded, your funding agency may request an Assurance/ Certification/Deform.) Check the following if needed:

□ Protection of Human Subjects Assurance/Certification/Declaration of Exemption (Formerly Optional Form – 310)

Assurance/Certification Attachments

OTHER REVIEW COMMITTEES

0 unresolved comment(s)

If you check any of the below committees, additional materials may be required with your application submission.

Does your research fall under the purview of any of the other review committees listed below? [If yes, check all that apply and attach applicable materials using the attachment button at the bottom of your screen.]

∩ Yes ∩ No

Additional Information

- □ Institutional Biosafety Committee
- □ Radiation Safety Committee
- □ Radioactive Drug Research Committee
- ☐ Markey Cancer Center (MCC) Protocol Review and Monitoring Committee (PRMC)
- ☐ Graduate Medical Education Committee (GME)
- ☐ Office of Medical Education (OME)
- Institutional Biosafety Committee (IBC) Attach required IBC materials
- Radiation Safety Committee (RSC) For applicability, see instructions and attach form
- Radioactive Drug Research Committee (RDRC)
- Markey Cancer Center (MCC) Protocol Review and Monitoring Committee (PRMC)*** - Attach MCC PRMC materials, if any, per instructions.
- Office of Medical Education (OME)
- Graduate Medical Education Committee (GME)

Attachments

** If your study involves cancer research, be sure to select "Cancer Research" in the "Research Attributes" section. ORI will send your research protocol to the Markey Cancer Center (MCC) Protocol Review and Monitoring Committee (PRMC). The MCC PRMC is responsible for determining whether the study meets the National Cancer Institute (NCI) definition of a clinical trial and for issuing documentation to you (the investigator) which confirms either that PRMC approval has been obtained or that PRMC review is not required. Your IRB application will be processed and reviewed independently from the PRMC review.

ADDITIONAL INFORMATION/MATERIALS

0 unresolved comment(s)

Do you want specific information inserted into your approval letter? c Yes 6 No

Approval Letter Details:

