Include a brief review of existing literature in the area of your research. You should identify gaps in knowledge that should be addressed and explain how your research will address those gaps or contribute to existing knowledge in this area. For interventional research, search PubMed and ClinicalTrials.gov for duplicative ongoing and completed trials with same condition and intervention(s).

Eyebrow ptosis commonly occurs with age and can result in significant patient distress with decreased visual fields, compromised activities of daily living, and aesthetic concerns. Operations to correct the ptotic brow date back to the early 1900's. Passot described excision of the skin and soft tissue directly above the lateral brow in 1930 and it has remained as a popular technique. Alternative procedures include coronal incision with lift, mid-forehead lift, and endoscopic brow lifts. The direct excision brow lift allows clear visualization of adjustments made in brow position and the impact on surrounding facial landmarks. It is also relatively quick and straightforward but it is often criticized for an unsightly facial scar. However, with proper skin closure techniques, studies have shown adequate patient satisfaction with their outcomes.

Given the prominent location of these scars and the associated social stigma, we feel it is important to focus on the skin closure methods. Skin closure is a critical portion of the operation and may be performed with sutures, skin glue, or staples. A trend has evolved utilizing skin glue (octyl-2-cyanoacrylate, Dermabond®) as it is thought to be faster, leading to shorter operating room times, potentially less cost, less risk for needle stick injuries, provides barrier to contamination, and does not require the sometimes painful suture removal. Sutures are thought to take more operating room time and require removal in outpatient clinic. There is also more variability with surgeon technique. Greene et al (1999) performed a study with the much thinner skin of the upper eyelids in blepharoplasties and found equivalent results in scar appearance, complications, and patient satisfaction. However, a Cochrane review to comparing tissue adhesives to skin glue found the latter actually took more time and was associated with more wound dehiscence. No studies looked at the use of these adhesives in the direct excision brow lift.

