Research Repositories: If the purpose of this submission is to establish a Research Repository (bank, registryou plan to collect is already available from a commercial supplier, clinical lab, or established IRB approved research repository, provide scientific justification for establishing an additional repository collecting duplicate material. Describe the repository design and operating procedures. For relevant information to include, see the UK Research Biospecimen Bank Guidance or the UK Research Registry Guidance.

The proposed study is a two staged prospective study comparing skin closure with octyl-2-cyanoacrylate (Dermabond) with conventional non-absorbable sutures in the direct excision brow lift.

In stage 1, subjects will be consented to receive one of two surgical closing techniques on a bilateral brow ptosis repair: 1) deep dermal sutures and superficial interrupted sutures (the standard of care at the University of Kentucky); or 2) deep dermal sutures and octyl-2-cyanoacrylate skin glue application for superficial closing. Subjects will undergo a single closing technique on both sides. Four subjects will complete surgery in each arm (n=8 subjects total: n=4 for arm 1, and n=4 for arm 2). After the follow-up period, the scar appearance between groups will be compared. If there the octyl-2-cyanoacrylate (dermabond) group have worse appearing scars, then we will not continue to study. If the difference in appearance is negligible, then we will return to the IRB for approval to advance to stage two.

Stage two is outlined below:

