Each patient will serve as their own control, with one brow undergoing skin closure with interrupted 6-0 prolene suture and the other with octyl-2-cyanoacrylate skin glue. Deep dermal sutures will placed in both wounds at 1 cm intervals. The patients will be randomized as to which side receives what type of closure (i.e. the right side receiving skin glue and the left receiving skin sutures or vice versa). This will prevent acquired bias during the scar analysis. The operation is done under monitored anesthesia care. We will record the time it takes to close both wounds. We will determine the precise costs of the skin glue and suture and the incurred costs per minute of operating room time. We will monitor the patients after discharge for any complications (infection, wound dehiscence, skin reaction, etc), which will be recorded. Patients will follow up at 10 days, and 3 months. Photos will be taken at the follow up visits with patient's consent. The scars will be aesthetically analyzed by plastic surgeons in terms of which scar is more aesthetically pleasing. In addition, the patient and observer (physician) will analyze the scar using the well established Patient and Observer Scar Assessment Scale. The physicians completing the forms are the research personnel.

Attachments

Subject Recruitment Methods & Advertising

Describe how the study team will identify and recruit subjects. Please consider the following items and provide additional information as needed so that the IRB can follow each step of the recruitment process.

- How will the study team identify potential participants?
- · Who will first contact the potential subjects, and how?
- Will you use advertisements? If so, how will you distribute those?
- How and where will the research team meet with potential participants?
- If applicable, describe proposed outreach programs for recruiting women, minorities, or disparate populations.
- How you will minimize undue influence in recruitment?
- · Attach copies of all recruiting and advertising materials (emails, verbal scripts, flyers, posts, messages, etc.).

For additional information on recruiting and advertising:

- IRB Application Instructions Advertisements
- PI Guide to Identification and Recruitment of Human Subjects for Research

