Informed consent will be obtained prior to enrollment in the study. The patient will undergo thorough history and physical examination in the clinic setting. We will then schedule for surgery if all criteria are met. The anesthesia staff will administer the standard and appropriate anesthetic. Local anesthesia will be administered. For step one of this research project the surgical procedure will be identical for all patients except the final superficial skin closure. We will design the amount of upper lateral superior brow tissue requiring excision to correct the patient's ptosis. Calipers will be used to ensure precise measurements. We will use a 15 blade to incise through the skin to the level of the frontalis muscle and fascia on both sides. Hemostasis will be achieved with Bovie electrocautery over the wounds. Both brows will be closed with 5-0 Vicryl in the subcutaneous and deep dermal layers spaced at 1 cm apart. The skin layer will be closed using interrupted 6-0 prolene sutures or with octyl-2-cyanoacrylate bilaterally. Patients will be randomized into either group. Photos will be taken both before the procedure and afterwards for research purposes. Then an independent group will evaluate photos and scar surveys for acceptability of results. The group will prepare a summary report. The photos and the summary report will be submitted to the IRB. If the the 6-0 prolene closure technique and octyl-2-cyanoacrylate closure technique are deemed to be equivocal, a request to move to Phase 2 will be made.

In phase 2 of the research project, a group of patients will all undergo the same procedure but each patient will be their own control. One side will be closed with interrupted 6-0 proline sutures and the other side closed with octyl-2-cyanoacrylate, it will be randomized what side will get which superficial skin closure.

Attachments

Data Collection & Research Materials

In this section, please provide the following:

- Describe all sources or methods for obtaining research materials about or from living individuals (such as specimens, records, surveys, interviews, participant observation, etc.), and explain why this information is needed to conduct the study.
- For each source or method described, please list or attach all data to be collected (such as genetic information, interview scripts, survey tools, data collection forms for existing data, etc.).

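### Randomising the side does not mask the scar raters: no scar rating in either stage is stated to be masked to closure, and the SAP analyses none that is

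*Combined protocol and SAP*

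**What the plan says.** **Stage 2 (Study Design).** Each patient has one brow closed with suture and the other with glue, and the side is randomised. The stated benefit is: "This will prevent acquired bias during the scar analysis". Two kinds of rating follow. The first is a preference judgement: "The scars will be aesthetically analyzed by plastic surgeons in terms of which scar is more aesthetically pleasing". The second is POSAS, completed by patient and physician, with the note: "The physicians completing the forms are the research personnel".

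**Stage 1 (Study Design, Research Procedures).** Patients are randomised to an arm, four per arm, and "Subjects will undergo a single closing technique on both sides". On progression: "If the difference in appearance is negligible, then we will return to the IRB for approval to advance to stage two". On review: "Then an independent group will evaluate photos and scar surveys for acceptability of results", followed by "The photos and the summary report will be submitted to the IRB".

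**Safeguards (Data and Safety Monitoring).** Photographs and surveys have identifiers removed before anyone outside the study team sees them. The surgeon's survey score is compared with the patient's to address conflict of interest. Results go to the IRB, which helps decide whether the study proceeds.

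**Analysis (SAP).** Only the POSAS survey given to patients, with demographic data, is used, and it is summarised descriptively.

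**The concern.** Bias that enters while scars are being judged is controlled by keeping the rater unaware of the treatment. Randomisation controls something else: which wound or patient gets which closure. A reader could take the quoted sentence to mean that rating bias has been dealt with, although the text describes no masking.

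Scar appearance is a subjective outcome, and the investigators state in advance that they expect the scars to be equivalent. In stage 1, appearance feeds the decision to stop or to ask the IRB to advance. It is also one of the four listed objectives, beside wound healing, cost and complications. A preference for either closure, in either direction, would add to the observed difference, and randomising side or arm would not remove it.

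**Working it through.** The plan gives no figure on this point to reproduce. The check is a short piece of algebra and a comparison of the sections.

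**1. What randomising the side does.** For one stage 2 patient and one rater, write the score difference as

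glue − suture = δ + S·λ + β

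Here δ is the true closure effect and λ the right-minus-left difference unrelated to closure. S is +1 if glue is on the right and −1 if on the left. β is any preference the rater attaches to a closure they know. If each side is equally likely, E[S] = 0 and the expected difference is δ + β. The side term goes and the rater term stays. β is zero by design only when the rater does not know the closure.

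Randomising S has a second, real benefit. With a fixed side, the side alone would reveal the closure and masked rating would be impossible.

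**2. Stage 1.** Both brows get the same closure, so there is no side randomisation. Arm randomisation balances patients in expectation, and the expected difference between arms is again δ + β.

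**3. Who rates or reviews the scars, and what is said about masking.**
- Plastic surgeons choosing the better scar (Study Design, stage 2): masking not stated.
- Physicians completing the observer POSAS (Study Design): research personnel, masking not stated.
- The surgeon's survey score (Data and Safety Monitoring; this may overlap with the previous item): masking not stated.
- The patient's POSAS (Study Design, Resources, SAP): masking not stated. The Background says that glue "does not require the sometimes painful suture removal", so patients can probably tell which closure they had. That is an inference.
- The independent group (Research Procedures, Data and Safety Monitoring): at least two people outside the study team, given de-identified material. Nothing says that closure is withheld.

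None of the five is stated to be masked. The form's Study Design prompt lists blinding among the features to describe, and the answer names none.

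**4. Whether the safeguards remove β.**
- *Removing identifiers* hides who the patient is. The text does not say that it hides the closure. The group also sees the surveys, in no stated order relative to the photographs, so scores from raters not stated to be masked may inform its view.
- *Comparing surgeon and patient scores* can expose a preference held by only one of them. If both know the closure and share a preference, it cancels: (δ + β) − (δ + β) = 0.
- *IRB review* adds outside judgement but is not stated to be masked.

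**5. Whether a size can be given.** The progression rule is verbal in all three sections that state it, with no margin on any scale. No size or direction of rater preference is given. A probability of a wrong stage 1 decision would rest entirely on assumed values, so none is reported.

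**6. Which ratings reach the analysis.** The SAP uses only patient-administered POSAS. Neither the plastic surgeons' judgement nor the independent group's assessment is included, so no rating stated to be masked is analysed.

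**The case against.** The strongest case against has four parts.

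- *Side randomisation does more than balance sides, and the text does not define acquired bias.* This stands. It removes side as a cue to closure, and the sentence may mean just that. A reader might infer that the randomisation is useless against rating bias. The documents do not support that reading; the fault is that a precondition for masking is presented as sufficient.
- *The sentence concerns stage 2, which the documents do not show was opened.* This also stands. Seven were enrolled against eight planned for stage 1, and the continuation review marks all activities complete. No inference about stage 2 data is warranted. The missing statement on masking covers stage 1 as well.
- *There are safeguards.* There are, and they count as partial. The independent group is the best of them, and it lacks only a statement that closure is withheld and that photographs are scored before surveys are seen.
- *Patients can hardly be masked, and patient POSAS is all that is analysed.* This limits what can be done for the closed study, but the rating should still be described as unblinded.

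A reader might also infer that the ratings were in fact biased, or that raters were in fact told the closure. The documents show only that masking is not stated; the data-collection attachments are not available to check. Nor is scar appearance the whole comparison, since three other objectives stand beside it.

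**Conclusion.** The concern holds in a limited form. Randomising the side balances side effects and removes side as a cue, but it is not masking, and the Study Design sentence claims more than it delivers. None of the five rating or review sources in either stage is stated to be masked to closure, the safeguards are not stated to conceal it, and the SAP analyses no masked rating. No size or direction of bias can be given.

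This rests on the available text being complete on masking. An attachment describing masked rating would change the finding for that rating.

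**What to change.** **For the study as closed.** Report POSAS as unblinded. This costs one sentence. A masked re-rating of any retained photographs, labelled retrospective, is optional. It may need new IRB approval, because the status page says approval can be inactivated and the Records section limits access to listed investigators.

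**For any continuation or future trial.**
- Reword the Study Design sentence: randomising the side balances side effects and removes side as a cue; masking is a separate step.
- Stage 1: have the planned independent group score coded photographs with closure withheld, before seeing any survey, from one named visit after suture removal. Use that score in the report to the IRB and add it to the SAP.
- Before that, reconcile the follow-up visits. Study Design gives 10 days and 3 months in its stage 2 text; Data and Safety Monitoring gives the week after surgery and six weeks. Also name the stage 1 photograph visit, since Research Procedures says only before and after the procedure.
- Stage 2, if opened: have the planned plastic surgeons judge coded photographs with side allocation withheld.
- Keep patient and research-physician POSAS as supporting outcomes, reported as unblinded.

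**Cost.** Reviewers, photographs, de-identification and subject numbers are already planned. The additions are a withheld closure key, a scoring sheet, a fixed photograph visit and the reconciled schedule. The downside is that photographs miss features that need touch, and some scars may still reveal the closure, so masking may be incomplete.

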In terms of monetary expenditures, one tube of octyl-2-cyanoacrylate costs approximately \$24. Macario et al site that one minute of operating room time costs approximately \$29, varying in case complexity. We would like to assess the total costs between the two techniques when time in the OR is taken into account.

We hypothesize that the scars will be equivalent in assessment and ultimately be less costly with less patient distress. We also suspect that the skin glue may create an occlusive barrier to infectious contamination of the wounds and potentially a lower complication rate.

Objectives

List your research objectives. Please include a summary of intended research objectives in the box below.

- 1. To determine if octyl-2-cyanoacrylate provides equivalent wound healing compared to conventional non-absorbable skin suture techniques
- 2. To determine if octyl-2-cyanoacrylate provides equivalent scar appearance compared to conventional non-absorbable suture techniques
- 3. To determine the cost effectiveness of the use of octyl-2-cyanoacrylate for skin closure compared to conventional non-absorbable suture techniques
- 4. To determine if octyl-2-cyanoacrylate results in equivalent complication rates compared to conventional non-absorbable suture techniques

Study Design

Describe and explain the study design (e.g., observational, secondary analysis, single/double blind, parallel, crossover, deception, etc.).

- · Clinical Research: Indicate whether subjects will be randomized and whether subjects will receive any placebo.
- Community-Based Participatory Research: If you are conducting community-based participatory research (CBPR), describe
 strategies for involvement of community members in the design and implementation of the study, and dissemination of results from
 the study.
- Qualitative research: Indicate ranges where flexibility is needed, if a fixed interview transcript is not available, describe interview
 topics including the most sensitive potential questions.

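### Objective 3 promises cost effectiveness, but the costing omits complication care, suture removal and any link to the scar result, so it is incomplete in an unknown direction

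*Combined protocol and SAP*

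**What the plan says.** The Objectives list as item 3: "To determine the cost effectiveness of the use of octyl-2-cyanoacrylate for skin closure compared to conventional non-absorbable suture techniques". The Background sets the scope: "We would like to assess the total costs between the two techniques when time in the OR is taken into account". It supplies two unit prices: "one tube of octyl-2-cyanoacrylate costs approximately" $24, and "one minute of operating room time costs approximately" $29.

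The inputs appear only in the stage-two part of Study Design. Time is measured ("We will record the time it takes to close both wounds") and then priced: "We will determine the precise costs of the skin glue and suture and the incurred costs per minute of operating room time". The next sentence covers harms: "We will monitor the patients after discharge for any complications (infection, wound dehiscence, skin reaction, etc), which will be recorded". No cost is attached to them there or elsewhere.

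The Background also says that sutures have to be taken out in clinic and that glue avoids this. No cost is given for removal either.

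Scar appearance and complications are separate objectives (2 and 4). The SAP statement at the end of the file confines the analysis to the POSAS survey and demographic data, summarised descriptively. It contains no cost analysis.

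**The concern.** A total-cost comparison should count each cost that differs between the two closures. Here at least two such costs are missing, and both arise after the patient leaves the operating room. One is the management of infection, dehiscence or skin reaction. The other is suture removal, which belongs to one side by definition. The priced items are cheap, so the missing ones need not be large to matter.

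The label is a second problem. Cost effectiveness relates a cost difference to a difference in outcome. The plan produces a cost difference and, separately, a scar result, and nowhere says how the two are to be read together. The investigators hypothesise that glue will be less costly. As written, the costing could neither confirm nor refute that for total cost, and could not support a statement about cost effectiveness.

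**Working it through.** The documents state no total-cost figure, so there is nothing to reproduce. The check asks how large the omitted costs must be to matter, and which way they point.

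**Inputs from the documents.** Tube $24; operating-room minute $29 (both Background).

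**Inputs not in the documents, assumed and shown as ranges.** Excess complication risk with glue, *d*, from −2% to +10%; cost per complication, *C*, from $200 to $3,000; cost of suture removal, *R*, from $0 to $150.

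**Step 1: scale.** 24/29 = 0.83 minutes, about 50 seconds. Ignoring the price of suture, a tube pays for itself if it saves that much closure time.

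**Step 2: what is priced and what is not** (glue minus suture, one brow of each, as in stage two).

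- Priced: (glue price − suture price) + 29 × (glue minutes − suture minutes).
- Unpriced: *d* × *C* − *R*.

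A positive unpriced amount means the omissions flatter glue; a negative one means they flatter suture.

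**Step 3: complication care alone.** Suppose a complication means re-closure taking 10, 20 or 30 minutes at the operating-room rate: 29 × 10 = $290, 29 × 20 = $580, 29 × 30 = $870. An excess risk of 1% to 5% then leaves out between 0.01 × 290 = $2.90 and 0.05 × 870 = $43.50 per glue brow. The excess risk that would equal the tube price is 24/290 = 8.3%, 24/580 = 4.1% or 24/870 = 2.8%.

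**Step 4: both omissions.** They flatter glue only if *d* exceeds *R*/*C*:

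| Removal cost *R* | *C* = $200 | $500 | $1,000 | $3,000 |
|---|---|---|---|---|
| $50 | 25% | 10% | 5% | 1.7% |
| $100 | 50% | 20% | 10% | 3.3% |

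With *C* = $1,000 and *R* = $50:

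- *d* = 2% gives 20 − 50 = −$30, which flatters suture.
- *d* = 10% gives 100 − 50 = +$50, which flatters glue.

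In operating-room time these are 30/29 = 1.0 and 50/29 = 1.7 minutes, both more than the tube price. Over the whole assumed grid the unpriced amount runs from −$210 (*d* = −2%, *C* = $3,000, *R* = $150: −60 − 150) to +$300 (*d* = 10%, *C* = $3,000, *R* = $0).

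**Step 5: the outcome side.** Objective 3 names cost effectiveness. The costing sentences name prices and minutes. The scar assessment in the same paragraph names aesthetic comparison and POSAS. No sentence joins them.

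**The case against.** A reader might infer that the costing is tilted towards glue, because the Background cites a review that "found the latter actually took more time and was associated with more wound dehiscence". The documents do not support that as a net statement, for five reasons:

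- The same costing omits suture removal, and that omission works against glue. In Step 3, any removal cost above $43.50 outweighs the whole complication range.
- The Background suspects that glue may lower the complication rate.
- Potential Risks & Benefits puts deep dermal sutures under both closures specifically to limit dehiscence.
- The review sentence sets one adhesive term against another and gives no rate, and the Background says that no study had examined these adhesives in this operation.
- The same review sentence reports longer time with glue, which the operating-room item would charge to glue.

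A reader might also infer that a cheaper closure with worse scars would be declared the winner. No such rule is written. Stage two is to be requested only if stage one shows a negligible scar difference, and scars and complications are objectives in their own right. That gate rests on four patients per arm and does not involve cost, so it does not supply the missing link.

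Finally, the practical reach is limited. Costing belongs to stage two, which needed fresh IRB approval, and the file is marked complete with 7 enrolled. This stands. It limits the urgency but leaves the defect in the plan.

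**Conclusion.** The point holds as a finding of incompleteness. The costing counts materials and operating-room minutes only, omits complication care and suture removal, and connects no cost to the scar outcome. It cannot answer objective 3 as worded.

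The net direction of the error is undetermined, since it depends on whether *d* × *C* exceeds *R* and the documents give none of the three. The only size that rests on the documents alone is the 0.83-minute equivalence of the tube, which shows how little it takes to reverse the comparison. Every other dollar figure above is illustrative. It depends on the assumed excess risk, cost per complication and removal cost and, in Step 3, on re-closure being charged at the operating-room rate. Comparing with the tube price also leaves out the suture price and the closure-time difference, which belong in the full contrast.

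**What to change.** In the stage-two part of Study Design, before any stage-two submission:

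1. For each brow, add the cost of managing every complication recorded for it (extra visits, materials, and any operating-room minutes at the same rate).
2. On the suture side, add the cost of suture removal. Say how a visit that would take place anyway is charged. Adding item 1 without item 2 would introduce a bias against glue.
3. Record closure time separately for each brow, since the present wording could be read as one time for the pair.
4. Report the paired cost difference with and without items 1 and 2.
5. Rename objective 3 as total cost per closure. Use *cost effective* only where the cost difference stands beside the POSAS and complication results.
6. Add this analysis to the SAP.

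For the completed stage, state that objective 3 was not addressed and make no cost claim.

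The change takes a few sentences and two more cost lines, and complications are already recorded. The downside is that rare, costly events will widen the interval for total cost, which is why both versions of the difference should be shown.
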